12.2.3 Change in satisfaction of hair coverage as reported by the patient

The patient satisfaction hair coverage questionnaire will be assessed by the patient. The patient might select one of the five numeric choices representing "very dissatisfied" (0) to "very satisfied" (4). For consistency with the satisfaction of hair coverage quality questionnaire (see Section 12.3), responses to the satisfaction of hair coverage questionnaire will be rated 1 ("very dissatisfied") to 5 ("very satisfied") in the summaries and by-patient data listing. Missing data will not be imputed.

Responses to patient satisfaction question will also be summarized based on the mITT analysis population by category, visit, and dosing regimen using count and percentage.

The patient satisfaction hair coverage will be further categorized as 'satisfied' (i.e., including responses of 'somewhat satisfied', 'mostly satisfied', and 'very satisfied') or 'dissatisfied' (i.e., including responses of 'dissatisfied' and 'very dissatisfied'). A shift table will be presented for change in satisfaction of hair coverage (satisfied vs. dissatisfied) as reported by the patient based on the mITT analysis population for each scheduled visit and each dosing regimen.

No supportive and subgroup analyses will be performed.

Patient satisfaction of hair coverage data will be displayed in a by-subject data listing.

12.3 Exploratory Efficacy Endpoint Analyses

12.3.1 Change in patient's eyebrows as measured by the patient's Visual Analog Scale (VAS)

The VAS is a distinct 100-millimeter line anchored on the left end at full degree of impairment (no eyebrow) and on the right end at no degree on impairment (full eyebrow). Indication of the degree of impairment perceived at the time of assessment is captured by marking the appropriate position on the line between the anchor points. The measured distance of the mark from the left anchor will be recorded in millimeters. To assess the degree of impairment, the VAS analysis value will be computed by subtracting the VAS recorded value from 100. Missing data will not be imputed.

The VAS for each eyebrow will be summarized based on the mITT analysis population by visit and dosing regimen using descriptive statistics. The change and percent change from Baseline in VAS will also be summarized similarly for each eyebrow. Difference of the means in change and percent change from Baseline between the two dosing regimens will be provided along with a two-sided 90% CI at each visit for each eyebrow.

No supportive and subgroup analyses will be performed for this endpoint.

	STATISTICAL ANALYSIS PLAN, Final v1.0
Protocol Number CP543.2003	Sponsor: Concert Pharmaceuticals, Inc.

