### 9.4. Visual Analog Scale (VAS) for Eyebrows

The visual analog scale is a scale of continuous measure initially developed for pain that has been used in a variety of clinical settings where the endpoint of interest is based on a subjective perception. The visual analog scale is a distinct 100 millimeter line anchored on the left end at full degree of impairment and on the right end at no degree of impairment, where indication of the degree of impairment perceived at the time of assessment is captured by marking the appropriate position on the line between the anchor points. The measured distance of the mark from the left anchor will be recorded in millimeters.

As specified in the Schedule of Events, patients will rate his/her eyebrows on the patient VAS. The left and right anchor points for the patient's eyebrow VAS are "None" and "Full", respectively. The patient VAS for eyebrows will measure the patient's eyebrows at the time of completion. An example of the patient VAS for eyebrows is provided in Appendix 16.3.

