6.2 Descriptive Statistics and Common Derivations

Continuous endpoints will be summarized using descriptive statistics (i.e., number of subjects with non-missing data, mean, standard deviation [SD], median, minimum and maximum). Categorical endpoints will be presented as frequencies and percentages. Unless otherwise indicated, the percentages will be computed based on the number of patients included in the concerned analysis population.

Summary tables will be presented by dosing regimen and visit, when applicable.

As the SALT score is by nature a measurement of total surface of the scalp without hair, it is important to note that in the context of this SAP, SALT endpoints will follow these definitions:

Absolute change from Baseline = difference in SALT measurements i.e., Baseline SALT score - post-Baseline SALT score

Relative change from Baseline = percent change of the post-Baseline SALT score, where baseline SALT score is the denominator i.e. (absolute change from Baseline / Baseline SALT score) * 100%

For all other endpoints (e.g., patient satisfaction hair coverage, VAS, patient satisfaction hair coverage quality, clinical laboratory, vital signs, etc.), the change and percent change from baseline will be computed as follows:

Change from Baseline = Assessment value at post-Baseline visit X – Baseline value.

Percent change from Baseline = (change from Baseline / Baseline value]) * 100%.

	STATISTICAL ANALYSIS PLAN, Final v1.0
Protocol Number CP543.2003	Sponsor: Concert Pharmaceuticals, Inc.

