6.4 Statistical Tests

No formal hypothesis tests will be conducted. Only two-sided confidence intervals (CIs) at the 90% coverage will be presented. Nominal p-values will be provided.

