	 Subgroup analyses: using LOCF imputation based on mITT analysis population within each subtype of alopecia areata at Baseline 	
Change from Baseline in satisfaction of hair coverage to Week 24	Baseline and Week 24	Descriptive statistics by visit and dosing regimen with difference in means and two-sided 90% CI (t-distribution) for each post-baseline visit
		• Main analysis: with no imputation based on mITT analysis population
		 Additional analysis: shift from baseline (satisfied vs. dissatisfied) to each post-baseline visit with no imputation based on mITT analysis population
		No supportive and subgroup analyses

	STATISTICAL ANALYSIS PLAN, Final v1.0
Protocol Number CP543.2003	Sponsor: Concert Pharmaceuticals, Inc.

Efficacy Endpoint	Collection Time	Method
Exploratory		
Change from Baseline in VAS for Eyebrows to Week 24	Baseline and Week 24	Descriptive statistics by visit and dosing regimen for each eyebrow separately with difference in means and two-sided 90% CI (t-distribution) for each post-baseline visit
		• Main analysis: with no imputation based on mITT analysis population
		No supportive and subgroup analyses
Change from Baseline in satisfaction of hair	Baseline and Week 24	Descriptive statistics by visit and dosing regimen with difference in means and two-sided 90% CI (t-distribution) for each post-baseline visit
coverage quality to Week		• Main analysis: with no imputation based on mITT analysis population
24		No supportive and subgroup analyses
Other		
Responder (80%) in relative change from Baseline in SALT score at	Baseline and Weeks 4, 8, 12, 16, 20, and 24	Count and proportion of subjects by visit and dosing regimen for each responder definition separately with difference in proportions and two-sided Wald 90% CI for each post-baseline visit
Weeks 4, 8, 12, 16, 20, and 24		 Main analysis: using LOCF imputation based on mITT analysis population
		• Supportive analysis: using LOCF imputation based on PP analysis population, if applicable
		• Subgroup analyses: using LOCF imputation based on mITT analysis population within each subtype of alopecia areata at Baseline

	STATISTICAL ANALYSIS PLAN, Final v1.0
Protocol Number CP543.2003	Sponsor: Concert Pharmaceuticals, Inc.

Efficacy Endpoint	Collection Time	Method

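### Percent change in eyebrow VAS uses a reversed baseline that can be zero or a few mm, so this added statistic is undefined for some patients and unstable for others

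*SAP*

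**What the plan says.** Protocol 9.4 sets the direction of the recorded scale: "The left and right anchor points for the patient's eyebrow VAS are 'None' and 'Full', respectively". A full eyebrow is therefore recorded at 100 mm. SAP 12.3.1 reverses this: "the VAS analysis value will be computed by subtracting the VAS recorded value from 100". On the analysis scale 0 is a full eyebrow and 100 is no eyebrow.

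SAP 12.3.1 continues: "The change and percent change from Baseline in VAS will also be summarized similarly for each eyebrow". It adds a comparison: "Difference of the means in change and percent change from Baseline between the two dosing regimens will be provided", with a two-sided 90% CI at each visit for each eyebrow, in the mITT population.

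SAP 6.2 defines the statistic as "Percent change from Baseline = (change from Baseline / Baseline value]) * 100" percent. The sentence introducing that formula names this endpoint: "For all other endpoints (e.g., patient satisfaction hair coverage, VAS, patient satisfaction hair coverage quality".

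The summary table in SAP 12.5 lists only change from Baseline in the eyebrow VAS, analysed "for each eyebrow separately with difference in means and two-sided 90% CI (t-distribution) for each post-baseline visit". Percent change does not appear there.

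**The concern.** A ratio to baseline needs a baseline that stays well away from zero. SALT has one, because entry requires a score of at least 50. The reversed eyebrow VAS does not:

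- The severity criterion (Protocol 7.1) concerns scalp hair only, and no inclusion or exclusion criterion asks for eyebrow loss.
- The mITT definition (SAP 4.1) requires a dose and one post-treatment SALT assessment. It sets no eyebrow condition.
- Totalis and universalis together are capped at about 75%, so about 25% or more of patients (about 15 of 60) have patchy or ophiasis disease. The study's definition of totalis/universalis does not itself require loss beyond the scalp.
- SAP 8 summarises eyelash/eyebrow involvement as a baseline characteristic, so it is expected to differ between patients.

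No text covers a zero denominator, sets a minimum baseline or defines an eyebrow-affected subset. SAP 6.3 and 12.3.1 say only that missing values are not imputed. At stake are the percent-change estimates and intervals: two eyebrows at two post-baseline visits (Weeks 12 and 24), four in all. Patients with little or no eyebrow loss, who have almost no room to improve, could have a large influence on them.

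**Working it through.** The documents give no baseline distribution, SD or expected effect for the eyebrow VAS, so there is no planned figure to reproduce. The check applies the SAP's formula and then varies what is unknown.

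**1. Formula.** With recorded marks R0 (baseline) and R1 (later visit), the analysis values are 100 - R0 and 100 - R1, and

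percent change = 100 × [(100 - R1) - (100 - R0)] / (100 - R0).

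**2. The same 5 mm worsening at different baselines.**

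| Recorded baseline (mm) | Analysis baseline (mm) | Percent change |
|---|---|---|
| 100 | 0 | undefined |
| 99 | 1 | +500% |
| 98 | 2 | +250% |
| 95 | 5 | +100% |
| 90 | 10 | +50% |
| 50 | 50 | +10% |
| 20 | 80 | +6.25% |

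Improvement cannot go beyond -100%, so the extreme values lie on the worsening side only. On the absolute scale every defined row is +5 mm, and so is the first.

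**3. One patient in an arm of 30.** Suppose 29 patients are at -50% and one goes from 2 mm to 7 mm: 100 × (7 - 2)/2 = +250%. The arm mean is (29 × -50 + 250)/30 = -1200/30 = -40%. Had that patient also been at -50%, it would be -50%.

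**4. Simulation of the whole comparison (assumptions, not document figures).** Two identical arms of 30. Affected patients have baseline impairment uniform on 40-100 mm and mean change -25 mm (SD 25). Near-full patients have baseline impairment uniform on 0-10 mm and only marking noise, SD 5 mm. Marks are rounded and bounded to 0-100.

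| Share near-full | SD of between-arm difference in mean percent change | Ratio to 0% |
|---|---|---|
| 0% | 9.3 points | 1 |
| 10% | 15.8 points | 15.8/9.3 = 1.7 |
| 20% | 20.1 points | 20.1/9.3 = 2.2 |
| 30% | 23.5 points | 23.5/9.3 = 2.5 |

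The corresponding SD for absolute change stays at about 5.9 mm. A near-full baseline rounds to 0 with probability 0.05, so the expected number of undefined values per trial of 60 is 60 × 0.10 × 0.05 = 0.3 at a 10% share and 60 × 0.30 × 0.05 = 0.9 at 30%.

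**5. A second set of assumptions.** Affected patients are recorded at 0-80 mm at baseline. Unaffected patients mark close to the full end, with an SD of 1 or 3 mm.

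| Share unaffected | Chance of at least one undefined value | Median 90% CI half-width, percent change (points) |
|---|---|---|
| 0% | 0 | 10.3-10.4 |
| 5% | 0.32-0.68 | 11.1-12.4 |
| 10% | 0.54-0.91 | 12.0-17.4 |
| 25% | 0.87-1.00 | 15.4-29.2 |

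The half-width for absolute change stays between 7.6 and 8.0 mm throughout. The direction agrees with step 4; the size depends on the share and on how exactly unaffected patients mark the line.

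**The case against.** The case for leaving this alone has real force.

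- **The endpoint survives.** The protocol and SAP define it as change in the patient's eyebrows on the VAS, not percent change. SAP 12.3.1 already plans absolute change with its own mean difference and CI, and SAP 12.5 lists only that. A reader might infer that an exploratory endpoint is lost; the documents do not support that.
- **The interval is not meaningless.** Only the individual patient's value is undefined. The mean and CI can still be computed on the remaining patients, with a loss of precision of about 1.7 to 2.5 times on the assumptions above.
- **Dramatic examples mislead.** A move from 2 mm to 20 mm gives +900%, but that is an 18 mm shift, or 18/5 = 3.6 SD of the assumed marking noise. It should not be presented as a few mm of noise.
- **Any loss of patients would be visible.** SAP 6.2 reports the number with non-missing data, and SAP Appendix 2 lists derived variables.
- **The share is unknown.** With up to about 75% totalis or universalis, few patients may have near-full eyebrows.
- **The stakes are low.** SAP 6.4 plans no formal hypothesis test: "Only two-sided confidence intervals (CIs) at the 90% coverage will be presented", with nominal p-values.

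All of this limits the consequence, but it does not supply the missing rule. A visible smaller n does not say who is left out or why, and near-zero baselines stay in the mean however the zeros are handled. Analysing the unreversed mark would not help either, since the zero denominator would move to patients with no eyebrows.

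**Conclusion.** The concern holds for the percent-change statistic only. Followed as written, SAP 12.3.1 and 6.2 give an undefined value at an analysis baseline of 0, dropped under no stated rule from an analysis described as mITT. At baselines of a few mm they give large positive values that carry undue weight in the arm mean. The algebra follows from the SAP alone and needs no assumption. The size does: the 1.7- to 2.5-fold rise in SD rests on assumed near-full shares of 10% to 30% and 5 mm marking noise, and it would vanish if every enrolled patient had substantial eyebrow loss, which nothing in the documents ensures. Absolute change in VAS, and with it the exploratory endpoint, is unaffected, as is the primary SALT analysis. This is a minor correction that costs almost nothing before unblinding.

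**What to change.** Delete percent change for the eyebrow VAS from SAP 12.3.1, both the summary and the between-regimen difference, and keep absolute change in mm with its 90% CI. The text then agrees with the SAP 12.5 table.

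If percent change is kept, restrict it, eyebrow by eyebrow, to those with a baseline VAS impairment above a numeric minimum fixed before unblinding, report medians, and show how many eyebrows fall outside. The involvement item in SAP 8 should not define the subset: it combines eyelashes and eyebrows, so it would admit patients with eyelash loss and full eyebrows.

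The cost is a few words of SAP text and one table shell. The downside is that one supplementary descriptive statistic is lost, or is shown on a subset.

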### 9.1. Demographic Characteristics and Medical and Surgical History

Demographic characteristics (i.e., sex, ethnic origin, date of birth) will be collected at the Screening Visit, between Day -28 and -1, and detailed on the eCRF.

The patient's alopecia areata will be classified by the Investigator into one of three categories defined for this study:

- 1) Alopecia areata: patchy type hair loss,
- 2) Alopecia totalis or universalis: complete hair loss on the scalp with or without body hair loss,
- 3) Alopecia ophiasis: band-like hair loss limited to the periphery of the scalp along the back of the hair line in the occipital region and possibly extending over each ear in temporal regions.

Key criteria that distinguish alopecia areata from other forms of hair loss may include abrupt onset of disease, a history of recurrence and spontaneous remission, response to topical or intralesional steroid treatment, and distribution of hair loss pattern. Care must be taken during the evaluation to assess for other causes of hair loss such as trichotillomania, or scarring alopecia and other forms of non-scarring alopecia. Evidence of thinning hair should be distinguished from pattern hair loss or telogen effluvium and evidence of inflammation should be investigated to rule out infection, as appropriate.

Thorough medical history, including current medications, nail and facial hair involvement, comorbidities, serious infection history and exposure risk, including HIV, as well as history or vaccination against herpes zoster will be collected at the Screening Visit, and at the Randomization Visit on Day 1.

Medical history should be thoroughly probed for potential exposure to serious infections such as HIV, history or vaccination against herpes zoster, as well as cancer risk due to the potential immunosuppressive properties of CTP-543 and known adverse events associated with JAK inhibitors.

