6.8 Adjustments for Covariates

Not applicable.

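### The exploratory eyebrow VAS comparison subtracts Day 1 VAS but does not adjust for it; ANCOVA would usually narrow the 90% CI at almost no cost, and percent change is not a safe substitute

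*SAP*

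**What the plan says.** The eyebrow VAS is an exploratory endpoint, recorded for each eyebrow at Day 1, Week 12 and Week 24 (Protocol Table 1; SAP Section 2). SAP 12.3.1 plans the between-regimen comparison as follows: "Difference of the means in change and percent change from Baseline between the two dosing regimens will be provided". The table in SAP 12.5 gives the method: "Descriptive statistics by visit and dosing regimen for each eyebrow separately with difference in means and two-sided 90% CI (t-distribution) for each post-baseline visit". SAP 6.8, on covariates, reads "Not applicable". SAP 6.4 adds: "Only two-sided confidence intervals (CIs) at the 90% coverage will be presented".

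Two derivations matter. In SAP 12.3.1, "the VAS analysis value will be computed by subtracting the VAS recorded value from 100", so the analysed value is impairment: 0 for a full eyebrow, 100 for none. SAP 6.2 defines "Percent change from Baseline = (change from Baseline / Baseline value]) * 100"%, so Day 1 impairment is the denominator.

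The analysis uses the whole mITT population, with no supportive or subgroup analysis. Entry depends on scalp loss (SALT of 50 or more; Protocol 7.1, criterion 4), and there is no eyebrow criterion. Randomisation is stratified by three alopecia subtypes (SAP 3.3). One of them pools totalis with universalis, described in Protocol 9.1 as "complete hair loss on the scalp with or without body hair loss".

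**The concern.** A patient with full eyebrows can enter but cannot improve, while a patient with none has the whole scale to gain. Change is therefore tied to the Day 1 value by the scale itself. A change score treats each millimetre of Day 1 difference as worth exactly one millimetre at follow-up. If patients regrow some fraction of what is missing, it is worth less than that, and subtraction over-corrects.

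Two things follow. Variation in eyebrow loss at entry stays in the error term and widens the interval. With about 30 patients per arm, a chance Day 1 difference between arms also shifts the reported regimen difference. Subtype stratification may help in part, but it classifies scalp pattern, eyebrow status can vary within the pooled stratum, and the planned interval does not use the strata. No formal test is planned, so the estimate and its interval are all that this comparison reports.

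**Working it through.** **Plan's own figure.** SAP 6.1 gives 25 completers per group, justified by the CI width for relative change in SALT. There is no SD or target width, so it cannot be reproduced, and no precision is stated for VAS. I take n = 25 per arm from it. Everything else below is assumed and shown as a range.

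**1. Interval width, equal SDs (σ) at baseline and follow-up, correlation ρ**

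- Change-score variance: 2σ²(1−ρ). ANCOVA variance: σ²(1−ρ²).
- Ratio: (1−ρ²)/[2(1−ρ)] = (1+ρ)/2. Width ratio: √[(1+ρ)/2].
- 90% half-width for change: t(0.95, 48) × √[2(1−ρ)] × √(2/25).
- 90% half-width for ANCOVA: t(0.95, 47) × √(1−ρ²) × √(2/25) × √(1+1/46), the last factor being an approximate small-sample penalty.

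| ρ (assumed) | √[(1+ρ)/2] | Narrower by | Half-width, change (σ) | Half-width, ANCOVA (σ) | Ratio at n = 25 |
|---|---|---|---|---|---|
| 0.3 | 0.806 | 19% | 0.561 | 0.458 | 0.82 |
| 0.5 | 0.866 | 13% | 0.474 | 0.415 | 0.88 |
| 0.7 | 0.922 | 8% | 0.367 | 0.343 | 0.93 |
| 0.8 | 0.949 | 5% | – | – | – |
| 0.9 | 0.975 | 2.5% | 0.212 | 0.209 | 0.99 |

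**2. Chance imbalance**

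If the arms differ by D in mean Day 1 VAS and the follow-up-on-baseline slope is b, the raw change difference is shifted by (1−b)D in size.

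- With 25 per arm, D has SD √(2/25) = 0.283 baseline SDs and exceeds 1.645 × 0.283 = 0.465 SDs in 10% of trials.
- Illustration: assumed baseline SD 39 mm and 30 per arm give 39 × √(2/30) = 10.1 mm. At b = 0.55 the shift is 0.45 × 10.1 ≈ 4.5 mm per standard error of D.

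**3. Simulation on the bounded scale**

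There were 25 per arm, no true regimen difference and 6,000 trials in each of 11 scenarios. A share of patients start full, a share start with none, and the rest are uniform over 0-100. Each recovers a random fraction of the loss, with measurement noise of SD 5 mm, and values are clipped to 0-100. Selected results:

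| Full / none at Day 1 | Mean regrowth | Slope b | Half-width, change (mm) | Half-width, ANCOVA (mm) | Ratio |
|---|---|---|---|---|---|
| 5% / 80% | 20% | 0.78 | 12.0 | 11.8 | 0.99 |
| 5% / 80% | 40% | 0.59 | 15.4 | 14.6 | 0.95 |
| 10% / 50% | 40% | 0.59 | 14.5 | 12.6 | 0.87 |
| 30% / 40% | 40% | 0.58 | 14.1 | 11.2 | 0.79 |
| 30% / 40% | 60% | 0.38 | 17.1 | 11.2 | 0.66 |

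Over the 11 scenarios the ratio ran from 0.66 to 0.99. Coverage was 0.895-0.907 for the change score and 0.897-0.904 for ANCOVA. The share of imbalance passed on, 1−b, was about 22%, 42% and 61% at mean regrowth of 20%, 40% and 60%.

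**4. Percent change**

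On the analysis scale a full eyebrow has baseline 0, so percent change divides by zero. If 5% of patients start at exactly 0, the chance of at least one among 50 is 1 − 0.95^50 = 0.92. Near zero it is unstable: the assumed 5 mm noise is 5 percentage points at baseline impairment 100 mm, but 5/2 = 250 points at 2 mm. The SAP gives no rule for either case.

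**The case against.** The case for leaving the plan alone has real substance.

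- **Baseline is already used.** A reader might infer that the plan ignores Day 1 VAS. It does not: change subtracts it and percent change divides by it. What is missing is adjustment.
- **Percent change already scales by room to improve.** On the impairment scale it is the proportion of loss recovered, and if patients regrow a fraction of what is missing, its mean does not depend on baseline. That holds away from zero. It fails for the patients who motivate the concern, those at or near full eyebrows, so it does not cure the problem.
- **The interval is valid.** Coverage stays near 90%, and randomisation removes bias on average. This stands: the loss is one of efficiency, plus a shift in the particular trial that is run.
- **The gain may be negligible.** Up to about 75% of patients may have totalis or universalis, so many may start with no eyebrows. With a responder/non-responder regrowth pattern, the interval narrows only 3-8% when 75% start near none and 5% full, and 2-6% when 85% start near none. This stands and sets the lower end of the range.
- **The endpoint is minor.** It is exploratory, the precision rationale concerns SALT only, and Protocol 11.4.4 asks for no specific VAS method. This stands and keeps the point optional.
- **The fix is selective and approximate.** No comparison in the SAP is adjusted, so VAS would be the exception, and one linear slope only approximates a bounded, perhaps bimodal, score. Both are true. ANCOVA nevertheless kept its coverage and was never wider on average in the scenarios run, and the scale limit gives this endpoint its own reason for adjustment.

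**Conclusion.** The point holds as an inexpensive improvement to an exploratory analysis. The unadjusted comparison is valid but usually wider than necessary, because it fixes at 1 a slope that regrowth on a bounded scale should pull below 1.

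The size rests on assumptions, since the documents give neither the VAS correlation nor the Day 1 distribution. With equal SDs, the ANCOVA interval is about 19% narrower at ρ = 0.3, falling to 5% at ρ = 0.8. On the bounded scale the gain runs from about 1-3% (most patients starting with no eyebrows, or high correlation) to over 30% (a wide spread at Day 1).

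A reader might go further and infer that the planned estimate is biased, or that a chance imbalance passes into it whole. Neither is supported. There is no bias on average, and only the share 1−b passes through, roughly 30-60% at assumed mean regrowth of 30-60%. Nor can it be said that most of the interval's width comes from differences at entry, because that depends on the unknown baseline mix.

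**What to change.** 1. In SAP 12.3.1 and the eyebrow row of SAP 12.5, make the between-regimen comparison for each eyebrow at Weeks 12 and 24 an ANCOVA of change in VAS on regimen and that eyebrow's Day 1 VAS. Report the adjusted mean difference with its two-sided 90% CI. Using the follow-up value as the response gives the same regimen difference.
2. Keep raw means and mean changes by regimen as description.
3. Amend SAP 6.8 to name Day 1 VAS as the covariate for this endpoint.
4. Do not use percent change for the between-regimen contrast. Otherwise limit it to patients with Day 1 impairment clearly above 0, with the cut-off fixed before unblinding.

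The cost is SAP wording and one model term (one degree of freedom). Day 1 VAS is already collected. The protocol leaves the VAS method to the SAP, so no amendment is needed.
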